6.8 R.T. Quality Assurance Reviews (8/13/15)

The Radiation Oncology Co-Chair, [name], will perform RT Quality Assurance Reviews. These reviews will be ongoing and performed remotely. RT Quality Assurance reviews will be facilitated by the ACR Core Laboratory/RTQA.

6.9 Radiation Therapy Adverse Events

Grade 3-4 (CTCAE, v. 4) therapy-induced mucositis and/or dysphagia, which are enhanced by cisplatin, are expected to develop in about two thirds of patients. Other common radiation adverse events include: fatigue, weight loss, regional alopecia, xerostomia, hoarseness, transient ear discomfort, dysgeusia, and skin erythema and desquamation within the treatment fields.

Less common long-term treatment adverse events include: hypothyroidism, loss of hearing, and chronic swallowing dysfunction requiring permanent feeding tube, and cervical fibrosis. Much less common radiation adverse events include: mandibular osteoradionecrosis (< 5% incidence with attention to the dental recommendations provided in Appendix VII), and cervical myelopathy (<1% with restriction of spinal cord dose to \leq 45 Gy).

6.10 Radiation Therapy Adverse Event Reporting

See Section 7.10 for details.

7.0 DRUG THERAPY

Institutional participation in chemotherapy studies must be in accordance with the Medical Oncology Quality Control guidelines stated in the RTOG Procedures Manual.

Protocol treatment must begin within 14 calendar days after randomization.

7.1 Code Breaks

The decision to break the code must be based on a life-threatening event or extraordinary clinical circumstance for which knowledge of drug assignment will affect clinical judgment. One of these criteria must be met for RTOG to consider breaking the treatment code.

During business hours (8:30 AM to 5 PM ET), call RTOG Headquarters at [contact] and ask to speak to the Supporting Study Statistician. For after hours, weekends, and holidays, call [contact].

7.2 Treatment (2/2/16)

7.2.1 Cisplatin:

Weeks 2-7 with concurrent radiation therapy and lapatinib/placebo: Patients will receive cisplatin, 100 mg/m², administered intravenously on days 8 and 29 of the treatment course (Note: cisplatin given within 24 hours of days 8 and 29, e.g. due to holidays, is acceptable). Weekends count as days. Cisplatin can be given before or after the fraction of radiation that is given on the same day. If radiation is held for more than 2 days (for any reason), cisplatin may be held as well until radiation therapy resumes.

See Section 7.6.1 for dose modification for weight loss. Use the actual body weight for all patients. Dose modification for obesity is not recommended.

7.2.1.1 High dose cisplatin is a highly emetogenic regimen with significant incidence of delayed nausea and vomiting. Institutional guidelines for highly emetogenic regimens should be followed. In the absence of such guidelines:

- For acute nausea and vomiting, premedication should include a 5-HT₃ antagonist, such as granisetron 1 mg iv.; ondansetron, up to 16 mg iv; or palonosetron, 0.25 mg

iv.; plus a corticosteroid, such as dexamethasone, up to 20 mg iv.. Palonosetron has a longer half life (40h) than the first generation 5HT3 antagonists.

- Breakthrough nausea and vomiting should be managed at the discretion of the medical or radiation oncologist. Delayed nausea and vomiting (greater than 24 hours after chemotherapy administration) may be managed by the addition of aprepitant concurrently or with metoclopramide and dexamethasone. Potential delayed nausea regimens include:
 1. The NK-1 antagonist, aprepitant (125 mg p.o.), may be added for prevention of delayed emesis on the day of cisplatin administration and for 2 consecutive days thereafter (80 mg, 80 mg p.o.), with a corticosteroid, such as dexamethasone on days 1, 2, and 3 after cisplatin. Dexamethasone should be reduced on day 1 to 12 mg and delivered at up to 8 mg total daily for up to 4 days total. 5HT3 antagonist (e.g. granisetron, ondansetron) may be given for 3 days, only if palonosetron was not given prior to chemotherapy. Fosaprepitant (115 mg iv. x 1) may be used instead of aprepitant on day 1, 30 minutes before cisplatin; if used, fosaprepitant may be used with or without aprepitant day 2 and 3, and dexamethasone will be given as described above.
 2. Delayed emesis also may be managed by the addition of dexamethasone 8 mg bid x 2 days, followed by dexamethasone 4 mg bid x 2 days, beginning day after chemotherapy; oral metoclopramide 0.5 mg/kg (usually 20-40 mg) in addition qid x 2-4 days; 5HT3 antagonist (e.g. granisetron, ondansetron) may be given for 3 days, only if palonosetron was not given prior to chemotherapy. Adjust dexamethasone downward if aprepitant was given in the preceding 4 days.

7.2.1.2 Patients must receive vigorous hydration and diuresis. A suggested regimen is pre-hydration with a 1 liter of D5N S over 2-4 hours and mannitol, 12.5 g iv. bolus immediately prior to cisplatin. Then cisplatin, 100 mg/m², in 500 ml NS is administered over 1-2 hours with an additional 1 to 1.5 liters of fluid given post-hydration. Any pre-existing dehydration must be corrected prior to cisplatin administration. Should extravasation occur, the treating physician should follow institutional guidelines for management.

Overnight hospitalization for hydration after cisplatin is strongly encouraged, if it is allowed by the patient's insurance company. Additional iv. hydration and BUN/creatinine check should be strongly considered later in the week after cisplatin administration, in order to prevent dehydration and severe fluid/electrolyte imbalance.

7.2.2 Lapatinib/Placebo: (1/16/14)

Note: See Section 7.2.2.1 for lapatinib/placebo feeding tube administration. See Section 7.6.2 for lapatinib/placebo dose modifications.

Week 1: Starting 7 calendar days prior to radiation, patients will take 6 lapatinib/placebo tablets (1500 mg) once daily, 7 days a week, by mouth or by feeding tube on an empty stomach (either 1 hour before or 1 hour after meals). Lapatinib/placebo tablets are **not** to be crushed.

Weeks 2-7: Concurrent with radiation and cisplatin, patients will take 6 lapatinib/placebo tablets (1500 mg) once daily, 7 days a week, by mouth or by feeding tube on an empty stomach (either 1 hour before or 1 hour after meals). Lapatinib/placebo tablets are **not** to be crushed.

After Concurrent Treatment (Maintenance): After completion of radiation, patients will continue lapatinib/placebo 6 tablets (1500 mg) once daily, 7 days a week, by mouth or by feeding tube on an empty stomach (either 1 hour before or 1 hour after meals) for 3 months.

Patient Diary: Patients will be asked to document daily lapatinib/placebo on a pill diary during concurrent treatment and maintenance, which will be collected by the institution as source documentation. Institutions will submit the DP form to RTOG at the end of concurrent treatment and every month during maintenance treatment (see Sections 11.2.3 and 12.1).

7.2.2.1 Recommended Dosing Procedure for Slurry Preparation of Lapatinib/Placebo Water Suspension

- Lapatinib tablets are NOT to be crushed.
- Place 120 mL (4 oz) of water in a glass container, then add 6 lapatinib/placebo tablets to the container. Cover the container, let it stand for 5 minutes, and then stir the

mixture intermittently for 10 minutes or until it is fully dispersed. Stir the mixture for 5 seconds then administer. Rinse the container with a 2 oz aliquot of water and repeat the administration process. This completes the administration process (total of 6 oz of liquid is dispensed).

7.2.2.2 Recommended Dosing Procedure for Slurry Preparation of Lapatinib/Placebo Kool-Aid Suspension

Prepare Lemonade or Tropical Punch Kool-Aid as directed on the package. Place 2 or 4 oz of Kool-Aid in a glass container, then add 6 lapatinib/placebo tablets to the container. Cover the container, let it stand for 5 minutes, and then stir the mixture intermittently for 10 minutes or until it is fully dispersed. Stir the mixture for 5 seconds then administer. Rinse the container with a 2 oz aliquot of water and repeat the administration process. This completes the administration process (total of 4-6 oz of liquid is dispensed).

7.3 Cisplatin (Cis-Diamminedichloroplatinum, DDP)

Refer to the package insert for additional information

7.3.1 Formulation: Each vial contains 10 mg of DDP, 19 mg of sodium chloride, 100 mg of mannitol, and hydrochloric acid for pH adjustment. One vial is reconstituted with 10 ml of sterile water. The pH range will be 3.5 to 4.5. Cisplatin injection also is available from the manufacturer in aqueous solution, each ml containing 1 mg cisplatin and 9 mg NaCl and HCL or NaOH to adjust pH.

7.3.2 Mechanism of Action: The mechanism of action of DDP has not been clearly elucidated; however, preliminary studies have indicated that the most likely mechanism of antitumor action of this drug resides in its ability to inhibit DNA synthesis and to a lesser degree, RNA and protein synthesis. It has also been shown that DDP binds to DNA and produces inter-strand cross-links. Also DDP is not phase-sensitive and its cytotoxicity is similar in all phases of the cell cycle.

7.3.3 Administration: Intravenous

7.3.4 Storage and Stability: Reconstituted solution of cisplatin is stable for 20 hours when stored at 27°C and should be protected from light if not used within 6 hours. The vials and injection should not be refrigerated. Cisplatin has been shown to react with aluminum needles, producing a black precipitate within 30 minutes.

7.3.5 Adverse Events: The following adverse events are anticipated:

- Hematologic: Myelosuppression, often with delayed erythrosuppression; rarely, acute leukemia;
- Gastrointestinal: Nausea, vomiting, anorexia, loss of taste;
- □Dermatologic: Alopecia;
- Renal: Elevation of BUN, creatinine and impairment of endogenous creatinine clearance, as well as renal tubular damage which appears to be transient); hyperuricemia, much more severe and prolonged adverse events have been observed in patients with abnormal or obstructed urinary excretory tracts;
- Hepatic: Hypomagnesemia, hypokalemia, hypocalcemia;
- Neurologic: Restlessness, involuntary movements, loss of coordination, seizures, peripheral neuropathy;
- Allergic: Flushing, bronchoconstriction, tachycardia, hypotension;
- Other: Ototoxicity (with hearing loss which initially is in the high-frequency range, as well as tinnitus); muscle cramps; weakness.

7.3.6 Supply: Cisplatin is commercially available.

7.4 Lapatinib/Placebo (Tykerb®; GW572016) IND 115409 (8/5/14)

This study will be conducted under an IND to be held by RTOG and will require FDA submission and approval. Lapatinib and placebo will be supplied to patients on study free of charge. Participating institutions can access the Lapatinib Investigator Brochure on the RTOG web site (password protected).

7.4.1 Chemical Name: N-{3-Chloro-4-[(3-fluorobenzyl)oxy]phenyl}-6-[5-({[2-(methylsulfonyl)ethyl]amino)methyl]-2 furyl]-4-quinazolinamine

7.4.2 Mode of Action: Dual inhibitor of epidermal growth factor receptor (EGFR or ErbB1) and ErbB2 tyrosine kinases.

7.4.3 How Supplied: Lapatinib and placebo are supplied as 250 mg oval, biconvex, orange film-coated tablets with one side plain and the opposite side debossed with FG HLS. The lapatinib

tablets contain 410 mg of lapatinib Ditosylate Monohydrate, equivalent to 250 mg lapatinib free base per tablet. The tablets are packaged into HDPE bottles with child-resistant closures. Excipients present in the tablet include: Microcrystalline cellulose, povidone, sodium starch glycolate, and magnesium stearate. The film-coat contains: Hydroxypropyl methylcellulose, titanium dioxide, triacetin/glycerol triacetate, and yellow iron oxide. Each bottle of lapatinib or placebo contains 90 tablets.

7.4.4 Administration: Oral on an empty stomach (either 1 hour before or 1 hour after meals).

7.4.4.1 Prohibited Medications

See Appendix VI.

7.4.5 Storage and Stability: The intact bottles should be stored at controlled room temperature (15°C-30°C). Shelf life surveillance studies of the intact bottle are on-going. Current data indicates lapatinib is stable for at least 2 years at controlled room temperature (15°C - 30°C).

7.4.6 Lapatinib Adverse Events

7.4.6.1 Cardiac: Cardiovascular events have been seen in patients taking other compounds that inhibit ErbB2 when used in combination with or following anthracyclines, and interstitial pneumonitis has been reported in patients taking compounds that inhibit ErbB1. See Sections 7.7.1 and 7.7.2 for management guidelines.

7.4.6.2 Hepatotoxicity: Hepatobiliary events have been seen in patients taking lapatinib and other tyrosine kinase inhibitors. See Section 7.7.3 for management guidelines.

7.4.6.3 Dermatologic

Significant skin adverse events (Grade 3 or more) resulting from lapatinib are rare (1-3%). For CTCAE, v. 4 Grade 4 rash manifested as toxic epidermal necrolysis (i.e. Stevens-Johnson's Syndrome etc) lapatinib must be permanently discontinued. See Section 7.7.4 for management guidelines.

7.4.6.4 Gastrointestinal

Experience thus far suggests that when lapatinib is used as monotherapy most diarrhea presents as uncomplicated CTCAE v. 4 grade 1 or 2 (G1 54%, G2 20%, G3 15%, G4<1%). In rare cases, diarrhea can be debilitating, and potentially life threatening if accompanied by dehydration, renal insufficiency, and/or electrolyte imbalances. Standardized and universal guidelines have been developed by an American Society of Clinical Oncology (ASCO) panel for treating chemotherapy-induced diarrhea (Benson, 2004). Early identification and intervention is critical for the optimal management of diarrhea. A patient's baseline bowel patterns should be established so that changes in patterns can be identified while the patient is on treatment. See Section 7.7.5 for management of nausea and/or vomiting and Appendix V for diarrhea management guidelines.

7.4.6.5 Interstitial Lung Disease

See Section 7.7.6 for management guidelines.

7.4.7 Supply: Lapatinib and matching placebo will be provided free of charge by Novartis and distributed by a vendor, Biologics, Inc., under contract to RTOG.

Each blinded, patient-specific bottle will be labeled with the following:

- The study number (i.e. RTOG 3501);
- The bottle number (i.e. Bottle 1 of 2 and Bottle 2 of 2);
- The number of capsules
- The patient ID number (e.g. 3501-YYY, where the study number and sequence number represents the unique patient identifier assigned by RTOG at registration);
- The patient's initials (i.e. first, middle, last);
- A blank line for the site pharmacist to enter the patient's name;
- Administration instructions (i.e. "Take xx tablets every day for xx days");
- Storage instructions (i.e. "Store at controlled room temperature, xx degrees");
- Emergency contact instructions.

7.4.8 Drug Ordering (2/2/16)

BLINDED (lapatinib or placebo) THERAPY

No blinded starter supplies will be available for this study. Blinded, patient-specific clinical supplies will be sent to the registering investigator at the time of randomization. This randomization will be performed by RTOG Headquarters. The patient ID number assigned by RTOG Headquarters must be recorded by the registering institution for proper study medication

dispersion. Once a patient has been registered, RTOG Headquarters will electronically transmit a clinical drug request for that patient to Biologics, Inc. This request will be entered and transmitted by RTOG Headquarters the day the patient is registered.

Upon receipt of patient randomization notification, Biologics will: 1) Check to confirm site has an active Study Agent Shipment Form (SASF): 2) Place a call to the study site confirming the order was received and arrange day and time of arrival for the study drug; 3) Ship the initial shipment of study drug as listed below:

7.4.8.1 *Initial Shipment:* 4 Bottles of study drug to be taken continuously beginning 1 week prior to RT (8 weeks at 1500 mg (6 tabs/250mg each) PO QD). Biologics will place a follow-up call at week 4 for subsequent shipment of maintenance therapy study drug. Subsequent shipments will be made as listed below.

7.4.8.2 *Subsequent Shipment:* 3 months for maintenance treatment (6 bottles: 3 months at 1500 mg (6 tabs/250 mg each) PO QD.

Drug requests received by Biologics prior to 2 PM ET Monday through Friday, will be processed and shipped that day. Drug requests received after 2PM ET Monday through Friday will be processed and shipped the next business day. See shipment schedule below.

RTOG 3501 Shipment Schedule				
Patient registered with RTOG	E-order transmitted by RTOG	E-order Received by Biologics	Order shipped by Biologics	Order received at site
Monday	Monday	Monday by 2PM ET	Monday	Tuesday
Tuesday	Tuesday	Monday after 2PM ET until Tuesday 2pm ET	Tuesday	Wednesday
Wednesday	Wednesday	Tuesday after 2PM ET until Wednesday 2pm ET	Wednesday	Thursday
Thursday	Thursday	Wednesday after 2PM ET until Thursday 2pm ET	Thursday	Friday
Friday	Friday	Thursday after 2PM ET until Friday 2pm ET	Friday	Monday
		Friday after 2PM ET	Monday	Tuesday

The SASF (available on the RTOG web site, www.rtog.org, under protocol-specific materials/regulatory resources) for U.S. and Canadian sites must be submitted to RTOG Headquarters ([contact]) or e-mail it to [contact] as soon as the individual responsible for the study agent has been identified.

All shipments will be sent by FedEx Priority Overnight delivery (delivery by 10:30AM to most US addresses. Packages will be tracked by Biologics until confirmed delivered and delivery exceptions are managed with the highest level of urgency to ensure therapy start date adherence. Packing slips with the shipment tracking number included will be faxed to the designated site coordinator for all shipments.

Questions about supply and delivery should be directed to:

**[name], Program Manager
Biologics, Inc.
Clinical Research Services**

7.4.9 Accountability

The Investigator, or a responsible party designated by the investigator, must maintain a careful record of the inventory and disposition of all agents received from Novartis. It is the responsibility of the Investigator to ensure that the agents are only dispensed to study patients. The agents must be dispensed only from official study sites by authorized personnel according to local regulations.

7.4.10 Drug Destruction

Opened bottles of lapatinib/placebo must be disposed of by incineration at the site as chemotherapy or biohazardous waste. At the completion of the study, all unused lapatinib/placebo also must be incinerated at the site. If the site is unable to dispose by incineration, opened bottles and/or unused lapatinib/placebo should be returned to Biologics, Inc. for destruction (see contact information above). It is the responsibility of the Investigator to ensure that a current record of agent disposition is maintained at each study site where agents are inventoried and disposed, including dates and quantities. Sites should complete the drug destruction form located on the RTOG web site, www.rtog.org, under protocol-specific materials/regulatory resources and send the form to Biologics (see above for contact information).

7.6 Dose Modifications (3/22/16)

7.6.1 Cisplatin Modifications, Day 29

7.6.1.1 Neutropenia: If on the day of scheduled treatment with cisplatin the absolute neutrophil count (ANC) is < 1200, hold treatment until ANC ≥ 1200, then treat at 100% dose. Neutropenic fever will require permanent 25% dose reduction. Per CTCAE, v. 4, febrile neutropenia is described as ANC < 1000/mm³ with a single temperature of >38.3 degrees C (101 degrees F) or a sustained temperature of ≥ 38 degrees C (100.4 degrees F) for more than 1 hour.

7.6.1.2 Thrombocytopenia: If on the day of scheduled treatment with cisplatin the platelet count is < 75,000, hold treatment until platelets are > 75,000, then treat at 100% dose. Thrombocytopenia that results in bleeding will require a 25% dose reduction.

7.6.1.3 Neurotoxicity: If any signs of grade 3 or greater neurotoxicity occur, discontinue cisplatin. Continue radiation therapy (RT) and lapatinib/placebo.

7.6.1.4 Renal Adverse Events: Cisplatin should be administered on the scheduled day of treatment using the following guidelines. **Note:** If creatinine is > 1.3 mg/dl, clearance must be calculated (Cockcroft-Gault) in order to make dose adjustment. If the calculated nomogram is 50 mL/min or above, a 24-hour urine collection is not needed, but if the calculation is less than 50 mL/min, a 24-hour urine collection is mandated and the cisplatin will be determined as follows:

Serum Creatinine	Creatinine Clearance	Cisplatin Dose
≤ 1.5 mg/dl OR	> 50 ml/min.	100 mg/m ²
> 1.5 mg/dl AND	40-50 ml/min.	50 mg/m ²
> 1.5 mg/dl OR	< 40 ml/min.	Hold drug*

*Cisplatin should be held (but RT continued), and the creatinine measured weekly. If the serum creatinine is < 1.5 mg/dl or creatinine clearance is > 50 ml/min, then the second dose of cisplatin can be given at the reduced dose of 50 mg/m². Also see Section 7.6.1.6 below.

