3.1 Conditions for Patient Eligibility (9/27/16)

3.1.1 Pathologically (histologically or cytologically) proven diagnosis (from primary lesion and/or lymph nodes) diagnosis of squamous cell carcinoma of the oropharynx, hypopharynx, or larynx;

3.1.2 For patients with an oropharynx primary, the tumor must be negative for p16 by immunohistochemistry;

3.1.3 Selected stage III or IV disease: patients with T2 N2-3 M0, T3-4 any N M0 are eligible; in addition, p16 negative oropharynx cancer T1 N2b, N2c, or N3; and hypopharynx cancer patients with T1-2 any N+ are eligible, including no distant metastases, based upon the following minimum diagnostic workup:

3.1.3.1 History/physical examination within 28 calendar days prior to registration, including an examination by a Medical Oncologist and Radiation Oncologist and documentation of the patient's weight;

3.1.3.2 Examination by an ENT or Head & Neck Surgeon, including laryngopharyngoscopy (mirror and/or fiberoptic and/or direct procedure) within 42 days prior to registration;

3.1.3.3 Chest CT scan, or PET/CT scan within 42 calendar days prior to registration to rule out metastatic disease;

3.1.3.4 Contrast enhanced CT scan or MRI or PET/CT scan of the tumor site and neck nodes within 42 calendar days prior to registration;

3.1.3.5 EKG and ECHO or MUGA scan within 84 calendar days prior to registration;

- 3.1.4 Zubrod Performance Status 0-1 within 14 calendar days prior to registration;
- 3.1.5 Age \geq 18;
- 3.1.6 CBC/differential obtained within 14 calendar days prior to registration, with adequate bone marrow function defined as follows:
 - 3.1.6.1 Absolute neutrophil count (ANC) \geq 1,500 cells/mm³;
 - 3.1.6.2 Platelets \geq 100,000 cells/mm³;
 - 3.1.6.3 Hemoglobin \geq 8.0 g/dl (Note: The use of transfusion or other intervention to achieve Hgb \geq 8.0 g/dl is acceptable.);
- 3.1.7 Adequate renal and hepatic function within 14 calendar days prior to registration, defined as follows:
 - 3.1.7.1 Serum creatinine < 1.5 mg/dl or creatinine clearance (CC) \geq 50 ml/min within 14 calendar days prior to registration, determined by 24-hour collection or estimated by Cockcroft-Gault formula:
 - CCr male = [(140 – age) x (wt in kg)]
[(Serum Cr mg/dl) x (72)]
 - CCr female = 0.85 x (CrCl male)
 - 3.1.7.2 Total bilirubin < 2 x the institutional ULN;
 - 3.1.7.3 AST or ALT \leq 3 x the institutional ULN;

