7.6.1.5 Other Adverse Events

- Mucositis: Significant mucositis from radiation and cisplatin is expected and will not be an indication for cisplatin dose modification. No cisplatin dose reductions will be made.

- Ototoxicity: For new clinical hearing loss not requiring a hearing aid or for tinnitus that interferes with activities of daily living, treat at 50% dose reduction. For hearing loss requiring a hearing aid, discontinue cisplatin. Continue RT and lapatinib/placebo.
- If the physician is unsure about the severity of the hearing loss, an audiogram is encouraged.

7.6.1.6 If the second dose of cisplatin is delayed more than 21 days because of hematologic or renal adverse events, that dose will be omitted.

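### The day 29 renal dose rows for cisplatin are not mutually exclusive: three of six creatinine-by-clearance combinations meet two rows, and a hold can already satisfy its own release condition

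*Combined protocol and SAP*

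**What the plan says.** Cisplatin 100 mg/m2 is "administered intravenously on days 8 and 29 of the treatment course" in both arms (7.2.1). The renal rule stands under the heading "7.6.1 Cisplatin Modifications, Day 29". Its Note (7.6.1.4) says "If creatinine is > 1.3 mg/dl, clearance must be calculated (Cockcroft-Gault) in order to make dose adjustment". No 24-hour collection is needed if the calculated value is 50 or above, but "if the calculation is less than 50 mL/min, a 24-hour urine collection is mandated". The table then has three rows:

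- 100 mg/m2: creatinine at most 1.5 mg/dl, **or** clearance above 50 ml/min.
- 50 mg/m2: creatinine above 1.5, **and** clearance 40-50.
- Hold: creatinine above 1.5, **or** clearance below 40.

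Under the footnote, radiotherapy continues during a hold, creatinine is measured weekly, and the second dose may be given at 50 mg/m2 on this condition: "If the serum creatinine is < 1.5 mg/dl or creatinine clearance is > 50 ml/min". Section 7.6.1.6 omits the dose altogether "If the second dose of cisplatin is delayed more than 21 days" for hematologic or renal reasons.

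**The concern.** A dose table should send each patient to one row. Here the first and third rows are both joined by OR, with creatinine on opposite sides of 1.5, so a patient can enter one row on creatinine and another on clearance. Two sites that follow the text exactly could give different doses of a nephrotoxic drug to the same patient, and for low clearance the two doses are full dose and none.

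There is a smaller analytic consequence. Section 7.8 scores chemotherapy delivery from per protocol to unacceptable deviation, and section 13.2.4 makes compliance with planned treatment a secondary endpoint. Where two rows apply, that score has no defined answer.

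**Working it through.** The plan gives no figure to reproduce; the check is logical, with the protocol's own Cockcroft-Gault formula used to see whether the combinations are reachable.

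**Step 1. Rows met by each combination** (conditions from the 7.6.1.4 table):

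| Creatinine (mg/dl) | Clearance (ml/min) | Rows met |
|---|---|---|
| at most 1.5 | above 50 | 100 |
| at most 1.5 | 40-50 | 100 |
| at most 1.5 | below 40 | 100 and hold |
| above 1.5 | above 50 | 100 and hold |
| above 1.5 | 40-50 | 50 and hold |
| above 1.5 | below 40 | hold |

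Three of six meet two rows. The 50 mg/m2 row requires creatinine above 1.5, which alone satisfies the hold row, so the reduction row can never apply by itself.

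**Step 2. Release.** Take creatinine 1.4 and measured clearance 38. Full-dose row: 1.4 is at most 1.5, met. Hold row: 38 is below 40, met. Footnote release: 1.4 is below 1.5, already met. The text supports 100 mg/m2, no dose, and 50 mg/m2 for one patient on one day.

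**Step 3. Are these values reachable?** Formula (3.1.7.1): (140 - age) x kg / (72 x creatinine), times 0.85 for women. Ages, weights and creatinine values are assumed.

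- Man 70 y, 55 kg, creatinine 1.4: 70 x 55 / 100.8 = 38.2.
- Woman 65 y, 60 kg, creatinine 1.4: 75 x 60 / 100.8 x 0.85 = 37.9.
- Man 65 y, 65 kg, creatinine 1.6: 75 x 65 / 115.2 = 42.3.
- Man 55 y, 75 kg, creatinine 1.6: 85 x 75 / 115.2 = 55.3.

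The first two fall in the 100-or-hold combination, and the third in the 50-or-hold combination, if the 24-hour collection agrees with the estimate. The fourth needs no collection and meets the 100 and hold rows.

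**Step 4. A narrower reading.** The table can be read as applying only after a calculated clearance below 50. The fourth patient then never reaches it, and the combination above 1.5 with clearance above 50 arises only if the collection comes out higher than the estimate. The other two overlaps remain.

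**Step 5. Check of the proposed rows.** Clearance below 40: hold. Clearance 40 to below 50: 50 mg/m2 if creatinine is above 1.5, otherwise 100. Clearance 50 or more: 100. Clearance not required (creatinine 1.3 or less): 100. Every patient meets exactly one row. A value of exactly 50 gets full dose, in line with the entry limit of at least 50 and with the Note, which asks for no collection there.

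**The case against.** The strongest reply is that the OR in the hold row is a slip for AND. With AND the three rows are exclusive, and the footnote makes sense, because every hold would then start from creatinine above 1.5. But the current text prints OR. With AND, every patient with creatinine above 1.3 and up to 1.5 would get full dose at any clearance, so the calculation that the Note requires above 1.3 for dose adjustment could adjust nothing in that range.

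It is also fair to say that a careful oncologist would not give full dose at a measured clearance of 38. That is probably so, but the written rule permits it.

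Two stronger readings are tempting. First, that the rows conflict everywhere above 1.3. They do not: creatinine above 1.3 and up to 1.5 with clearance of 40 or more means full dose, and creatinine above 1.5 with clearance below 40 means hold. Nor is the 24-hour collection pointless at creatinine 1.4, since it separates 40-50 from below 40.

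Second, that full dose with clearance never assessed is an error. Entry accepts "Serum creatinine < 1.5 mg/dl or creatinine clearance" as alternatives, calculation is required only above 1.3, and no renal dose rule is written for day 8. A woman of 75 y, 50 kg, creatinine 1.0 has an estimated clearance of 65 x 50 / 72 x 0.85 = 38.4 that nobody need calculate. The documents do not show that this is wrong. It is a chosen criterion, and nothing bars a site from calculating. There are also safeguards not limited to day 29: "Patients must receive vigorous hydration and diuresis" (7.2.1.2), dehydration must be corrected before cisplatin, creatinine or clearance is tested every 7 days (Appendix I), and Appendix V holds chemotherapy for persistent grade 2, complicated, and grade 3 or 4 diarrhea. These do not identify low clearance at normal creatinine, so the point merits thought, but as policy and not as correction.

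**Conclusion.** The table in 7.6.1.4 is wrong as written. Three of six combinations carry two instructions, the 50 mg/m2 row never stands alone, and the release condition can be true at the moment of holding. This rests on the printed OR and AND and on no clinical assumption; on the narrower reading in step 4, two overlaps still hold without further condition.

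The 3 of 6 counts combinations, not patients. The documents give no weights or creatinine values for enrolled patients, so the number affected is unknown and may be small. A reader might infer an effect on the primary comparison. The documents do not support that: the rule is the same in both blinded arms. The defect concerns safety, consistency between sites, and the scoring of compliance.

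**What to change.** Amend the table and footnote in 7.6.1.4:

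1. Hold: clearance below 40, whatever the creatinine.
2. 50 mg/m2: creatinine above 1.5 with clearance from 40 to below 50.
3. 100 mg/m2: clearance 50 or more; or creatinine at most 1.5 when clearance is 40 or more or was not required.
4. Release a hold on repeat clearance, keeping the footnote's limit of above 50, and not on creatinine alone.

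Cost: some patients with creatinine at most 1.5 and clearance below 40 are held who might now get full dose, and release needs a repeat clearance. In the other direction, patients with creatinine above 1.5 and clearance of 40 or more are dosed where a site might now hold; the sponsor should confirm that this is intended.

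For the sponsor to consider separately: calculating Cockcroft-Gault before each dose, including day 8, from data already collected. Each value below 50 would add a 24-hour collection. The age at which the estimate equals 50 is 140 - 72 x 50 x creatinine / (kg x sex factor). At creatinine 1.0 and 50 kg this is 68.0 for men and 55.3 for women, so collections start at 69 and 56. At creatinine 1.3 and 70 kg it is 73.1 and 61.3, so 74 and 62. A day 8 rule would also have to say what happens to a held first dose.

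The benefit is limited to patients still to be dosed. Section 13.5 projected the end of accrual around March 2017, and 13.6.3 the end of concurrent therapy around July 2017.
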